7.3.2 Visit 2: 3 Hour Visit/Exit

- The subject will be asked to score their subjective response according to the CVJ defined 0-10 Grading scales. Lens preference will be recorded.
- •
- The lenses will be removed and retained.
- •
- The subject will be discharged and will sign the exit statement.

7.3.3 Summary of Visits and Procedures

Table 2 summarizes the visits and procedures for the study.

	Visit 1	Visit 3
Informed Consent	~	
Meet inclusion/exclusion criteria	~	
History at baseline	~	
Demographics	~	
Instillation of lens at office	~	
Subjective assessments	~	~
Lens fit assessments	~	~
	~	 ✓
Exit study		✓

Table 2: Summary of Visits and Procedures

8 Adverse Event Reporting

8.1 Adverse Event Definitions

An 'adverse event' refers to any undesirable clinical occurrence in a participant, whether it is considered to be device-related or not. Adverse events (AE) may be classified as 'unanticipated adverse device effects,' 'serious adverse events,' 'significant adverse events,' or 'non-significant adverse events,' as defined below.

Classification	Definition
Serious Adverse Event	Those events that are life-threatening, or result in permanent impairment of a body function, or permanent damage to a body structure or necessitate medical (therapeutic) or surgical intervention to preclude permanent impairment of a body function or permanent damage to a body structure.
Significant Adverse Event	Those non-serious adverse events that occur with contact lens usage that are not sight-threatening but are usually symptomatic and may warrant therapeutic management and /or temporary or permanent discontinuation of contact lens wear.
Non-Significant Adverse Events	Those less severe non-serious adverse events that occur with contact lens usage that are not sight-threatening, may or may not be symptomatic and may warrant palliative management, such as ocular lubricants or temporary interruption of contact lens wear.
Unanticipated Adverse Device Effect	Adverse events in a clinical trial that were not previously identified in the protocol in terms of nature, severity, or degree of incidence. An Unanticipated Serious Adverse Device Effect is an unanticipated adverse event that is serious in nature and caused by or associated with the device and is considered reportable.

AE classification, coding (for reporting to the sponsor) and examples are provided in the following

table of Contact Lens Adverse Event Classification and Reporting table:

Code	Condition	Reporting	
Serious Adverse Events			
01	Presumed infectious keratitis or infectious corneal ulcer		
02	Permanent loss of \geq 2 lines of best spectacle corrected visual acuity (BSCVA)		
03	Corneal injury that results in permanent opacification within central cornea (6mm)	Notify sponsor as	
04	Uveitis or Iritis (e.g. presence of anterior segment inflammation as described in ISO 11980, Annex B)	soon as possible, within 24 hours;	
05	Endophthalmitis	IRB reporting as	
06	Hyphema	per requirements	
07	Hypopyon		
08	Neovascularization within the central 6mm of cornea		
00	Other serious event		
Signific	ant Adverse Events		
11	Peripheral (outside central 6mm), non-progressive, non-infectious ulcer		
12	Symptomatic corneal infiltrative event		
13	Superior epithelial arcuate lesions (SEALs) involving epithelial split	Notify sponsor as	
14	Corneal staining ≥ dense coalescent staining up to 2mm in diameter (e.g. moderate, ISO 11980 grade 3)	soon as possible, within 5 working	
15	Corneal neovascularization ≥ 1.0mm vessel penetration (e.g. ≥ ISO 111980 Grade 2), if 2 grade change from baseline	days; IRB reporting as per	
16	Any temporary loss of ≥ 2 lines BSCVA for ≥ 2 wks	requirements	
17	Any sign and/or symptom for which subject is administered therapeutic treatment or which necessitates discontinuation of lens wear for ≥ 2 weeks		
10	Other significant event		
Non-significant Adverse Events			
21	Conjunctivitis (bacterial, viral or allergic)		

Confidential

22	Papillary conjunctivitis if ≥ mild scattered papillae/follicles approximately 1mm in diameter (e.g. ISO 11890 Grade 2), if 2 grade change from baseline	Notify sponsor as
23	Asymptomatic corneal infiltrative events	soon as possible, within 5 working
24	Any sign and/or symptom for which temporary lens discontinuation for > 1 day is recommended (if not already classified)	days; IRB reporting as per
20	Other sign and/or symptom warranting classification as a non-significant adverse event	requirements

Normal or adaptive symptoms

Transient symptoms such as end-of-day dryness, lens awareness, itching or burning or other discomfort may occur with contact lens wear and may occasionally reduce wearing time. *These are not reported as adverse events unless in the investigator's opinion they are unexpected in nature, severe or have a high rate of occurrence.*

This clinical study will also ascertain satisfaction or preference with subjective attributes such as comfort, vision, or lens handling. Responses to these subjective questionnaires will not be considered as Adverse Events.

8.2 **Procedures for Adverse Events**

Treatment of an adverse event will depend on its nature and severity. Based on the clinical judgment of the investigator the subject may be referred to an ophthalmologist for treatment. The investigator will attempt to determine whether the reaction is related to the test device or a result of other factors. An Adverse Event Form will be completed for each adverse event. If both eyes are involved, a separate Adverse Event Form will be completed *for each eye*. Whenever possible, the adverse event will be photo-documented.

Expenses incurred for medical treatment as part of study participation will be paid by the sponsor (bills and prescription receipts kept). The subject must be followed until resolution and a written report completed indicating the subsequent treatment and resolution of the condition.

8.3 Reporting Adverse Events

All potential Serious and Unanticipated Adverse Device Effects that are related or possibly related to subject participation will be reported to the Principal Investigator and the sponsor within 24

hours of the investigator becoming aware of the event. The Principal Investigator will report the event to the IRB as soon as possible (by fax, mail/delivery, phone, or email). All fatal or life threatening events will be reported immediately to the IRB.

Significant and Non-Significant Adverse Events will be reported to the sponsor as soon as possible, but no later than 5 working days after the occurrence.

8.4 Discontinuation from the Study

A subject's study participation may be discontinued at any time if, in the opinion of the sponsor or the investigator it is in the best interest of the subject. All discontinuations will be fully documented on the appropriate study forms and the Discontinuation Form will be completed.

9 Device Malfunctions

A device malfunction means the failure of the device to meet its performance specification or otherwise perform as intended. *Any defective lens that is likely to cause or contribute to a Serious Adverse Event should be reported to the Principal Investigator and the sponsor within 24 hours of the investigator becoming aware of the malfunction.*

Other defective lenses should be reported to the Sponsor as soon as possible.

This clinical study will also ascertain satisfaction or preference with subjective attributes such as comfort, vision, or lens handling. Responses to these subjective questionnaires will not be considered as complaints or Device Malfunctions.

10 Statistical Analysis

10.1 Statistical analysis

Summary statistics will be produced (e.g. mean, standard deviation).

and subjective scores between study lens types. $\chi 2$ test will be used to compare the fitting performance between study lens types. The critical alpha level for statistical significance will be set at p ≤ 0.05 , with adjustment for multiple comparisons.

All participants who were evaluated will be used in the analysis. In the event of missing data, individual data points will be excluded in the analysis and not extrapolated from the collected data.

11 Data Quality Assurance

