Study Implementation document:

CLINICAL EVALUATION OF MYDAY LENSES

Sponsor Study Code:

Version Number:

Implementation document Date:

Sponsor Company:

Document Type:

Study Category:

[figure not shown]
Clinical Sites:

Implementation document Sponsor:	Date:
	Date:

PERSONNEL & FACILITTIES

Confidential Protocol Version 2.0: JP-MKTG-201709_02

Protocol Synopsis

Protocol / Study Number	JP-MKTG-201709_02
Title	Clinical Evaluation of CooperVision MyDay [®] Lenses
Name of Device(s) and (by USAN material)	MyDay [®] (stenfilcon A), 1-DAY ACUVUE [®] TruEye [®] (narafilcon A)
Indications for Use	Approved for use:
	stenfilcon A. (Single use daily wear)
	narafilcon A. (Single use daily wear)
	Indication for use in this study:
	3 hours of single use daily wear
Study Design	3 hours, single masked, randomized, contralateral, single use daily wear, non-dispensing study.
Purpose	The aim of this non-dispensing study is to evaluate the fitting performance of MyDay Compared it with 1-DAY ACUVUE® TruEye in a range of spherical powers.
Study Duration	The anticipated timeline for this study is as follows:
	Patient enrolment: February 2018
	Visits: V1 (Baseline), V2 (After 3 hours of lens wear/Exit visit)
Patient Population	Adapted spherical soft contact lens wearers with myopia that provide written informed consent and meet protocol entry criteria.
Sample Size	Target enrollment and completion of 40 subjects total.
Clinical Site Destination	Japan
Number of Clinical Sites	4 Sites
Patient Follow-up	Patients enrolled in this study will be followed up:
	Follow-up: 3 hours of lens wear/Exit visit
Primary Endpoints	Objective: Lens fitting characteristics, such as Lens movement, Horizontal lens centration, Vertical lens centration, Corneal coverage, Lens lag, Overall fitting performance, Investigator Fit Preference
Secondary Endpoints	Subjective: Subjective rating of wearing comfort, dryness, stinging/burning, edge awareness/lens awareness, and lens preference

TABLE OF CONTENTS

1	Intro	oduction5	
2	Stu	dy Objective6	
	2.1	Study Hypothesis	6
3	Stu	dy Design6	
4	Ethi	ics Review / Statement of Compliance6	
	4.1	Relevant Standards / Guidelines	6
	4.2	Institutional Review Board	7
	4.3	Informed Consent	7
5	Pote	ential Risks and Benefits to Human Subjects7	
6	Mat	erials and Methods8	
	6.1	Participants	8
	6.2	Study Materials	9
	6.3	Visit Schedule and Procedures1	1
7	Adv	verse Event Reporting12	
	7.1	Adverse Event Definitions1	2
	7.2	Procedures for Adverse Events1	4

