2.1 Study Hypothesis

The study primary hypothesis is that there will be no differences between the Test and Control lenses in term of fitting characteristics.

3 Study Design

This will be a non-dispensing, randomized, contralateral study comparing a test lens against an appropriate control lens. Each subject will be randomized to wear the test lens in one eye and the control lens in the other eye. It is anticipated that this study will involve up to 2 visits.

4 Ethics Review / Statement of Compliance

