7.2 Study Materials

7.2.1 Contact lens

Subjects will be randomized to receive either the Test or Control lens as a matched pair at each visit per a predetermined randomization schedule. The Test lenses used in this study will be

Confidential

provided by the Sponsor. The Control lenses will be sourced by the site. Details of the contact lenses are shown in Table 1.

	MyDay (Test)	TruEye (Control)
Material	stenfilcon A	narafilcon A

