7.3 Visit Schedule and Procedures

7.3.1 Visit 1: Baseline Visit

Procedures to be Performed

The following evaluations will be performed to assess eligibility according to the Inclusion and Exclusion Criteria at the baseline visit only:

- The study lenses will be fitted according to the randomization table.
- Subjective ratings on insertion will be recorded according to the CVJ defined 0-10 scales. Lens preference will be recorded.
- The study pair of contact lenses will be allowed to settle for 5 minutes.
- The subject will be asked to score their subjective response according to the CVJ defined 0-10 scales. Lens preference will be recorded.
- Lens fit will then be assessed and graded according to the CVJ defined Grading scales.
- The subject will be discharged and asked to return for a follow-up visit after 3 hours.

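### Section 10.1 plans a χ2 test of primary lens fit without naming a paired or ordered form, although each subject wears both lenses and fit is graded

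*Combined protocol and SAP*

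**What the plan says.** The synopsis describes the study as "3 hours, single masked, randomized, contralateral, single use daily wear, non-dispensing study". Section 3 says "Each subject will be randomized to wear the test lens in one eye and the control lens in the other eye". With the target of 40 subjects, each fit item gives 40 pairs of eyes.

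Fit is the primary endpoint. The synopsis lists movement, horizontal and vertical centration, corneal coverage, lag, overall fitting performance and Investigator Fit Preference. Section 7.3.1 says "Lens fit will then be assessed and graded according to the CVJ defined Grading scales". The number and meaning of the grades are not given. Section 2.1 states the primary hypothesis that "there will be no differences between the Test and Control lenses in term of fitting characteristics".

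Section 10.1 says a χ2 "test will be used to compare the fitting performance between study lens types", at p ≤ 0.05 with adjustment for multiple comparisons. It does not say whether the test is paired, whether it uses grade order, how grades are grouped, or which visit is tested. Table 2 in section 7.3.3 ticks "Lens fit assessments" in both visit columns. Missing data points are dropped singly, with no rule for a subject who has only one eye graded.

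Two features of the text limit what can be concluded. The sentence before the χ2 sentence survives only as "and subjective scores between study lens types", so its test and first subject are not visible. And section 7.2.1 says "Subjects will be randomized to receive either the Test or Control lens as a matched pair at each visit", which does not match the one-lens-per-eye allocation in the synopsis and section 3.

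**The concern.** Two eyes of one person share lid tension, corneal shape and tear film, and here also the same examiner and occasion, so their fit grades are likely to be positively correlated. An ordinary χ2 on a lens-by-grade table counts 80 independent eyes. It overstates the variance of the test-control difference, and its p-values come out too large. It also gives the same answer however the grades are ordered, so it spreads its power over patterns that nobody expects.

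Both features reduce the chance of detecting a real difference in fit. Because the primary hypothesis is absence of a difference, the error runs in the direction of that hypothesis.

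**Working it through.** **Stated figure.** The plan gives no power, effect size, rates, correlation or margin, so there is no calculation to reproduce. What follows is illustration.

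**From the documents:** 40 pairs; alpha 0.05 (taken as two-sided, before multiplicity adjustment).
**Assumed:** fit rates, grade distribution, and between-eye correlation 0, 0.3 or 0.5. Correlation is throughout that of an underlying bivariate normal (latent) variable cut into grades.

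**1. Why the ordinary χ2 is conservative.** With a common rate p in both eyes, Pearson χ2 uses variance 2p(1−p)/n for the difference. The true variance is 2p(1−p)(1−φ)/n, where φ is the correlation of the two binary results. Approximate size is therefore 2[1 − Φ(1.96/√(1−φ))]. At p = 0.70, latent 0.3 gives φ = 0.182 and size 3.0%; latent 0.5 gives φ = 0.318 and size 1.8%.

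**2. Two-level fit, exact over all tables of 40 pairs.** Pearson χ2 (no continuity correction) against mid-p McNemar, where p = 2P(X ≤ k) − P(X = k), X ~ Bin(d, ½), d is the number of discordant pairs and k the smaller discordant count (p = 1 if the two discordant counts are equal). Results at latent correlation 0 / 0.3 / 0.5; differences are taken before rounding.

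| Case | χ2 | mid-p McNemar | Difference (points) |
|---|---|---|---|
| Type I error, 70% in both | 4.8 / 3.0 / 1.8% | 4.7 / 4.5 / 4.3% | |
| Type I error, 95% in both | 4.3 / 3.3 / 2.3% | 1.5 / 1.2 / 0.9% | |
| Power, 60% v 80% | 50 / 50 / 50% | 48 / 56 / 62% | −1 / +6 / +13 |
| Power, 70% v 90% | 63 / 64 / 65% | 60 / 66 / 73% | −3 / +2 / +8 |
| Power, 85% v 95% | 35 / 34 / 32.5% | 27 / 29 / 31% | −8 / −5 / −2 |

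Hand check, 60% v 80% at latent 0.5: the discordant share is 0.324, so the true SD of the difference is √((0.324 − 0.2²)/40) = 0.0843. Pearson null SE is √(2 × 0.7 × 0.3/40) = 0.1025, and power is Φ((0.2 − 1.96 × 0.1025)/0.0843) = Φ(−0.01), about 50%. McNemar null SE is √(0.324/40) = 0.0900, and power is Φ((0.2 − 1.96 × 0.0900)/0.0843) = Φ(0.28), about 61%.

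**3. Five ordered grades (5/20/50/20/5%), 0.5 SD shift, simulated with 20,000 replicates.** Power at latent correlation 0 / 0.3 / 0.5:

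- ordinary χ2: about 30 / 28 / 24%
- paired χ2 that ignores order (Stuart-Maxwell): about 26 / 35 / 47%
- Wilcoxon signed-rank: about 52 / 66 / 78%

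A separate run of 5,000 replicates gave 28/28/25%, 24/36/47% and 52/66/77%. At correlation 0 the whole gain comes from grade order, since Stuart-Maxwell gains nothing there. At 0.5, pairing takes power from 24% to 47%, and order takes it from 47% to 78%.

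**4. Items with a central optimum (for example movement, if graded too loose to too tight).** Signed-rank on raw grades tests a shift and has about 5% power when one lens only has wider spread. Signed-rank on distance from the optimum has about 9 to 10% power for a pure 0.5 SD shift, against 24 to 30% for the ordinary χ2. No single choice suits every difference.

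**The case against.** **The χ2 may be a paired one.** McNemar, Stuart-Maxwell and Bowker are all χ2 tests. This stands. A reader might infer that the plan prescribes an invalid unpaired test; the text does not say so, and every loss above depends on the ordinary reading. But a test whose form is unnamed can be chosen after the data are seen, and a paired χ2 would still ignore order in items with more than two ordered grades.

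**Text is lost just before the χ2 sentence.** It may have named a test for other measures, or a paired test for some fit items. The χ2 might even be meant only for the single item of overall fitting performance. This limits certainty about which items are affected. The χ2 sentence for fit is itself complete.

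**Section 7.2.1 describes a matched pair.** The finding rests on the allocation in the synopsis and section 3. If subjects instead wore one lens type in both eyes, the direction of the error could change, so the passages need reconciling.

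**The gain is not uniform.** It is not. Near ceiling the paired test has less power in the cases run and is itself conservative. A reader might also infer gains of up to 30 points for two-level fit at correlation 0.5. That holds only if 0.5 is φ between the binary results, which corresponds to a latent correlation of about 0.79 to 0.92 in these cases. On the latent scale used for the grades, the change at 0.5 is +13, +8 and −2 points.

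**It is a feasibility study.** No power is claimed, and the error does not raise false positives. That limits the severity. But 10.1 still sets a significance level for a stated primary hypothesis.

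**Conclusion.** The concern holds as a gap in specification that should be fixed. The visible plan for primary fit names neither pairing nor order, in a design that supplies both. If the ordinary form is used and the eyes are positively correlated, the primary p-values are too large. In the illustration at latent correlation 0.3 to 0.5, size falls to 3.0 to 1.8% for two-level fit at 70%. Power relative to a paired test changes by between +5 and −13 points for two-level items. For five ordered grades, the ordinary test has about 28 to 24% power against 66 to 78% for signed-rank, much of that gap coming from order.

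These sizes rest on assumed rates, grades and correlations; the documents give none of them. Confidence is moderate because of the lost text and the conflict with section 7.2.1. A reader might infer that a paired test would make a non-significant result evidence of no difference. It would not: no margin is stated, and the test would still only fail to reject.

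**What to change.** In section 10.1, replace the χ2 sentence with text to this effect:

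- Eye-level fit grades are compared within subject, with the pair of eyes as the unit of analysis.
- Items graded from worse to better: Wilcoxon signed-rank test, or a cumulative-logit model with a subject effect.
- Items with a central optimum: Stuart-Maxwell test. If signed-rank on distance from the optimum is preferred for an item, fix that before the data are seen, given its low power for a pure shift.
- Two-level items: mid-p McNemar test.
- Each paired difference is reported with a 95% confidence interval.
- Investigator Fit Preference, naturally one response per subject, keeps a one-sample test (χ2, or exact binomial among subjects with a preference).
- A subject with one eye missing for an item is left out of that item's paired test.

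Also list which item falls in which type, name the visit tested, and reconcile the matched-pair wording of section 7.2.1 with the synopsis and section 3.

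The cost is a short edit and slightly more analysis work, with no new data or subjects. The statistical price is some power on two-level items when the eyes are nearly uncorrelated or fit is near ceiling, up to about 8 points in the cases run.

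### The chi-square test for fit uses neither the pairing of fellow eyes nor the randomized allocation group, which costs precision but does not bias the lens comparison

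*Combined protocol and SAP*

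**What the plan says.** The synopsis and Section 3 describe a contralateral design: "Each subject will be randomized to wear the test lens in one eye and the control lens in the other eye". The sample size is given as "Target enrollment and completion of 40 subjects total", that is, 40 eyes per lens. Lens fit is the primary endpoint, and Section 2.1 hypothesizes no difference between the lenses.

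In Section 10.1 the readable fit analysis is a chi-square that "test will be used to compare the fitting performance between study lens types". It mentions no pairing, eye, allocation group or insertion order. The sentence before it survives only as "and subjective scores between study lens types", so its test, and whatever was listed before the word *and*, cannot be read.

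On allocation, Section 7.3.1 says "The study lenses will be fitted according to the randomization table". No ratio, blocking or insertion order is stated. Section 7.2.1 words the randomization differently: "Subjects will be randomized to receive either the Test or Control lens as a matched pair at each visit per a predetermined randomization schedule". For timing, Section 7.3.1 says "The study pair of contact lenses will be allowed to settle for 5 minutes", after which subjective scores are taken and fit is graded. Table 2 also lists fit assessment at the later visit.

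**The concern.** A contralateral trial is efficient because each subject is their own control. A chi-square on 80 eyes classified by lens treats the two eyes of a subject as independent. When fellow eyes resemble each other, its standard error is too large: the test rejects too rarely when the lenses are the same and misses real differences more often. That matters for a hypothesis of no difference, because avoidable noise makes a non-significant result easier to obtain and less informative.

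The second omission is the allocation group. If right and left eyes differ in graded fit for any reason, the difference enters the Test-minus-Control difference with opposite signs in the two groups. Left out of the analysis, it adds error, and in a realised sample with unequal groups it shifts the estimate by chance.

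**Working it through.** **Inputs.** From the documents: 40 subjects, one Test eye and one Control eye each, alpha 0.05. The documents give no power, effect size, fit rates, fellow-eye correlation or eye effect, so there is no planned figure to reproduce. Everything else here is assumed, and the tests are two-sided at 0.05 before any multiplicity adjustment.

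**Why the proposed contrast works.** Let τ be the Test-minus-Control effect and e the right-minus-left effect.
- Mean right-minus-left difference: e + τ in the Test-right group, e − τ in the Test-left group. Subtracting gives 2τ, and e cancels whatever the group sizes.
- Crude mean of Test minus Control: τ + e(nA − nB)/40, where nA and nB are the group sizes.

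**Chance shift of the crude contrast.**
- 20:20: zero.
- 26:14 with e = 10 points: 10 × 12/40 = 3.0 points. With e = 20 points: 20 × 12/40 = 6.0 points.
- If allocation is unblocked, with Binomial(40, 0.5): 24:16 or worse has probability 27%, 26:14 or worse 8%, and exactly 20:20 12.5%. The shift is equally likely in either direction, so it averages to zero.

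**Power for a binary fit grade.** Simulated at 20:20, 80% v 60% good fit, 20,000 runs per row:

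| Latent correlation | Eye effect (points) | Chi-square | McNemar (paired) | Paired, allocation-adjusted |
|---|---|---|---|---|
| 0.5 | 0 | 49.3% | 62.2% | 63.5% |
| 0.5 | 20 | 49.2% | 57.7% | 64.7% |
| 0.7 | 0 | 49.2% | 73.1% | 74.1% |
| 0.7 | 20 | 49.2% | 64.6% | 72.6% |

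- Gain from pairing (McNemar minus chi-square): 12.9 and 23.9 points with no eye effect; 8.5 and 15.4 points with a 20-point eye effect.
- Further gain from the eye term: 1.3 and 1.0 points with no eye effect; 7.0 and 8.0 points with a 20-point eye effect.

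**Type I error** (80% good fit with both lenses). At 20:20 with no eye effect, the chi-square rejects about 2% (correlation 0.5) or 1% (correlation 0.7) of the time. At 26:14 with correlation 0.5 it rejects 3.1% for a 10-point eye effect and 6.7% for a 20-point one; the adjusted contrast rejects about 5% in both.

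**Effect of the eye term alone on the named test.** The pooled variance is inflated by p(1 − p)/[p(1 − p) − e²/4]. For p = 0.8 and e = 0.20: 0.16/(0.16 − 0.01) = 1.067. For p = 0.8 and e = 0.10: 0.16/(0.16 − 0.0025) = 1.016. With p = 0.5 the factors are 1.042 and 1.010. For the chi-square, then, the eye effect adds only about 1% to 7%.

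**If fit is analysed as a paired numeric grade instead.** With e in SDs of the within-subject difference, the variance factor over random allocation is 1 + e²: 1.0625 at 0.25 SD and 1.25 at 0.5 SD. For a true difference of 0.45 SD and unblocked allocation, simulated power at 0.5 SD is about 70% unadjusted and 78% adjusted. At 0.25 SD adjustment gains 1 to 2 points. With no eye effect it costs about 1 point (79.5% v 78.4%).

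**The case against.** **The larger fault is pairing, not the eye term.** This stands. For the test actually named, omitting the eye term matters little, and most of the gain comes from using the pair.

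**A reader might infer bias or an inflated error rate.** The documents do not support either. Randomizing the eye leaves the crude contrast unbiased over repeated 1:1 allocation. A type I error of about 11% can be produced, but only for a paired numeric test that the readable plan does not name, a 0.5 SD eye effect that the documents do not give, and a 26:14 split that has 8% probability or less. Under the same assumptions 24:16 gives about 6%, and the average over unblocked allocation is a nominal 4.9%.

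**A reader might infer that insertion order follows the lens.** Section 7.3.1 has one shared settling period, and lenses inserted in sequence would settle for slightly different times. But no section says that eyes are handled in sequence, in what order, or that any site inserts the Test lens first. Any such gap is also small against the 3 hours before the later fit assessment.

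**Some relevant text is not visible.** Balance and order may be set in the randomization table, and the broken sentence in Section 10.1 may name another test for some fit measures. If the schedule is balanced, the chance shift disappears apart from dropped data points. Nor can it be said that the eye is the only thing randomized, because Section 7.2.1 conflicts with Section 3.

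**This is a small feasibility study.** True, and it limits the weight of the point. It does not justify discarding information that the design already collects.

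**Conclusion.** The point holds as an inexpensive gain in precision. The fit test that can be read in Section 10.1 leaves out both the pairing and the allocation group. Under the assumed 80% v 60% good fit and latent correlation of 0.5 to 0.7, using both raises power from about 50% to about 64% to 74% with the same 40 subjects. The eye term's own share runs from about 1 point to 8, depending on an eye effect that nobody has specified. For a paired numeric grade its share is 1 to 2 points at 0.25 SD and about 8 at 0.5 SD.

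All these sizes are illustrative. Multiplicity adjustment across the fit measures would lower every power figure. The conclusion does not depend on the randomization being unbalanced or on any particular insertion order. It does depend on the contralateral design in Section 3 being the one used.

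**What to change.** 1. In Section 10.1, replace the chi-square for fit with a within-subject analysis by allocation group. Form each subject's right-minus-left fit difference and compare it between the Test-right and Test-left groups, by a rank-sum test for grades or a paired model with an eye term.
2. For investigator fit preference, compare the share of subjects whose right-eye lens is preferred between the two groups, for example with Fisher's exact test.
3. Reconcile Section 7.2.1 with Section 3 on what is randomized, and state whether the schedule is balanced 1:1 on eye.
4. Optionally, in Section 7.3.1 fix the order of insertion and grading by eye (for example, right first) so that order cannot follow the lens. Any order effect then becomes part of the eye effect and is removed with it.

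The cost is wording in the analysis section, one line of procedure and one degree of freedom: about 1 point of power for a numeric grade if there is no eye effect. No extra subjects or visits are needed.

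### Fit is hypothesised not to differ, yet it is tested with an undefined multiplicity adjustment over an open list of measures, and any such adjustment makes non-significance easier to reach

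*Combined protocol and SAP*

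**What the plan says.** **Primary endpoint (Protocol Synopsis).** The objective primary endpoint is given as "Lens fitting characteristics, such as Lens movement, Horizontal lens centration, Vertical lens centration, Corneal coverage, Lens lag, Overall fitting performance, Investigator Fit Preference". Seven measures are named. They are introduced as examples, so the list is not closed, and none is ranked first.

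**Hypothesis (section 2.1).** The primary hypothesis is that "there will be no differences between the Test and Control lenses in term of fitting characteristics". No equivalence margin appears in the documents.

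**Timing.** At Visit 1, after 5 minutes of settling, section 7.3.1 says: "Lens fit will then be assessed and graded according to the CVJ defined Grading scales". In section 7.3.3, Table 2 ticks "Lens fit assessments" in both visit columns. The second column is headed Visit 3, although the study has two visits. No primary time point is named.

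**Analysis (section 10.1).** A chi-square "test will be used to compare the fitting performance between study lens types". The significance level is fixed at 0.05, and the same sentence adds "with adjustment for multiple comparisons". That sentence is complete. It names no adjustment method, no family (fit measures only, or the subjective scores too) and no count of tests.

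**Size (synopsis).** "Target enrollment and completion of 40 subjects total". No power, effect size, variability or sample-size rationale is given.

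**The concern.** In a trial that sets out to show a difference, lowering the per-test level makes the sponsor's claim harder to reach. In this plan the hypothesised result is no difference. Lowering the level makes each fit comparison more likely to come out non-significant, and a non-significant result looks like agreement with section 2.1. The safeguard therefore favours the hypothesis, so the problem goes beyond an unnamed method.

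The gaps compound this. With an open list, two apparent time points and no stated family, the divisor is not fixed by the plan. A fit difference with p = 0.02 is significant at 0.05. As the smallest p-value it is not significant under Bonferroni or Holm over 7 tests (threshold 0.0071) or 14 tests (0.0036). The same data could be reported as a difference or as support for the hypothesis, depending on a number the plan does not state.

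**Working it through.** There is no power figure in the plan to reproduce. The check therefore illustrates how far an adjustment could move the result.

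**Inputs from the documents**
- 40 subjects, each with one lens type per eye, so 40 pairs (synopsis; section 3).
- Level 0.05 (section 10.1). Two-sided is assumed, as sidedness is not stated.
- Seven named fit measures (synopsis). With one time point m = 7. With both time points ticked in Table 2, m = 7 × 2 = 14.

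**Inputs assumed**
- Bonferroni, because the method is not stated.
- A paired t-test on the within-subject difference, with true difference d in SDs of the paired differences: 0.3, 0.45 and 0.6.

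**Step 1. Per-test level**
- 0.05/7 = 0.0071
- 0.05/14 = 0.0036

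**Step 2. Power**

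Power = P(T > t_crit), where T is noncentral t with 39 degrees of freedom and noncentrality d × √40. The opposite tail is negligible. The critical values are 2.023 (level 0.05), 2.839 (0.05/7) and 3.101 (0.05/14).

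| d (assumed) | d × √40 | Level 0.05 | 0.05/7 | 0.05/14 |
|---|---|---|---|---|
| 0.3 | 1.90 | 46% | 19% | 13% |
| 0.45 | 2.85 | 79% | 51% | 41% |
| 0.6 | 3.79 | 96% | 82% | 75% |

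At 0.45 SD, the chance of missing a real difference on one measure rises from 21% to 49% (m = 7) or 59% (m = 14). The difference detectable with 80% power grows from 0.45 SD to 0.59 or 0.63 SD.

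**Step 3. Does the pattern depend on the t-test?**

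The plan uses chi-square, so two checks on proportions were run, again with assumed rates:
- Chi-square, 40 eyes per lens, 90% versus 65% acceptable fit: 77%, then 50% (m = 7), then 40% (m = 14).
- Exact McNemar, 40 pairs, discordant proportions 30% and 5%: 74%, then 42%, then 34%.

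The direction and rough scale are the same.

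**Step 4. What adjustment protects against**

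If no measure truly differs and the tests are independent, the chance of at least one false positive without adjustment is:
- 1 − 0.95^7 = 30%
- 1 − 0.95^14 = 51%

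So adjustment has a proper use when a difference is claimed. The converse matters here. With 14 such tests, the chance that every one is non-significant is 0.95^14 = 49% unadjusted and (1 − 0.05/14)^14 = 95% adjusted.

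**Step 5. What an interval would show**

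For a paired mean difference in 40 pairs, the half-width of an unadjusted 95% interval is 2.023/√40 = 0.32 SD. That tells the reader which differences the data leave open. A non-significant adjusted p-value does not.

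**The case against.** The strongest reply is that the adjustment is sound in itself. Unadjusted testing of this many measures would carry a false-positive risk of up to 51% in the independent case, and section 10.1 never says that non-significance will be taken as proof of no difference. Section 2.1 may simply state the null. If non-significance is misread, the deeper fault is the missing margin. This is also a feasibility study by its own description (section 2), with no power claim to lose. Much of this stands: the adjustment should be kept for claims of difference, and the stakes are moderate. But the plan pairs formal tests with a no-difference hypothesis and gives no other rule for judging it, so the misreading is the natural one.

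Three stronger readings are tempting, and the documents do not support them:

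- **That the adjustment roughly halves power.** This needs Bonferroni, about 14 tests and a starting power near 70–80%, none of which is in the plan. In Step 2, 0.45 SD with 7 tests loses about a third (79% to 51%), and 0.6 SD with 14 tests loses about a fifth (96% to 75%). Holm would usually lose less, and a family that includes the subjective scores would lose more.
- **That there are at least 14 primary comparisons.** No text says each measure is tested at each visit. The second fit assessment rests on the tick in Table 2, because the legible 3-hour procedures (section 7.3.2) do not list it. Investigator Fit Preference may be a single judgement per subject rather than a between-lens comparison. Text is missing from sections 7.3.2 and 10.1. That is not counted against the plan, but it leaves the number of tests uncertain.
- **That the family will be chosen after the data are seen.** The documents do not say when it will be fixed. They only fail to fix it here.

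**Conclusion.** The point holds in this form: a no-difference hypothesis without a margin is tested over an open, unranked list of fit measures with an undefined adjustment, and any lowering of the per-test level makes apparent support for that hypothesis more likely. The direction follows from the text and needs no assumption beyond the ordinary meaning of adjusting for multiple comparisons.

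The size is conditional. Under Bonferroni with 40 pairs, the illustrated power losses run from 14 percentage points (0.6 SD, 7 tests: 96% to 82%) to 38 points (0.45 SD, 14 tests: 79% to 41%). The effect sizes, the method and the family are all assumed, and the paired t-test stands in for the planned chi-square.

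This should be corrected because it changes what the trial can conclude. As a feasibility study with no stated power, it does not fail on this point.

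**What to change.** In section 10.1 and the synopsis:

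1. Close the list of primary fit measures by deleting *such as*, and state at which visits each is analysed.
2. Report each fit measure as a within-subject test-minus-control difference with an unadjusted 95% confidence interval. If Investigator Fit Preference is one judgement per subject, report the share preferring test minus the share preferring control, with its interval.
3. Apply multiplicity adjustment (for example Holm, over a stated family) only to claims that a difference exists.
4. State that non-significance, adjusted or not, will not be taken as showing that the lenses do not differ. If the sponsor wants to claim equivalence, it needs a margin set in advance. The documents give no basis for choosing one here.
5. Preferably, name one lead fit measure and time point in advance, tested at two-sided 0.05. Overall fitting performance at 3 hours is one candidate, but the choice is the sponsor's, and nothing in the documents marks that measure as the decisive one.

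The cost is a few sentences of text, slightly more reporting and a more cautious conclusion. If item 5 is adopted, the remaining measures become supportive. No subject, visit or procedure is added, since Table 2 already provides for fit assessment at both visits.
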